7.1.2.2 Full Physical Exam

The investigator or qualified designee will perform a complete physical exam during the screening period. Clinically significant abnormal findings should be recorded as medical history. A full physical exam should be performed during screening,

7.1.2.3 Directed Physical Exam

For cycles that do not require a full physical exam per the Trial Flow Chart, the investigator or qualified designee will perform a directed physical exam as clinically indicated prior to trial treatment administration.

7.1.2.4 Vital Signs

The investigator or qualified designee will take vital signs at screening, prior to the administration of each dose of trial treatment (on day 1 prior to MK-3475) and at treatment discontinuation as specified in the Trial Flow Chart (Section 6.0). Vital signs should include temperature, pulse, respiratory rate, weight and blood pressure. Height will be measured at screening only.

7.1.2.5 Eastern Cooperative Oncology Group (ECOG/Zubrod) Performance Scale

The investigator or qualified designee will assess ECOG status (see Section 12.1) at screening, prior to the administration of each dose of trial treatment and discontinuation of trial treatment as specified in the Trial Flow Chart.

7.1.2.6 Tumor Imaging and Assessment of Disease

For the purposes of this study, patients should be re-evaluated for response after cycle 2 (6 weeks) and then every 2 cycles (6 weeks). In addition to a baseline scan, confirmatory scans should also be obtained at least 4 weeks following initial documentation of objective response.

RECIST version 1.1* will be used in this study for assessment of tumor response. While either CT or MRI may be utilized, as per RECIST 1.1, CT is the preferred imaging technique in this study.

* As published in the European Journal of Cancer:

- PET-CT At present, the low dose or attenuation correction CT portion of a combined PET-CT is not always of optimal diagnostic CT quality for use with RECIST measurements. However, if the site can document that the CT performed as part of a PET-CT is of identical diagnostic quality to a diagnostic CT (with IV and oral contrast), then the CT portion of the PET-CT can be used for RECIST measurements and can be used interchangeably with conventional CT in accurately measuring cancer lesions over time. Note, however, that the PET portion of the CT introduces additional data which may bias an investigator if it is not routinely or serially performed.
- Conventional CT and MRI This guideline has defined measurability of lesions on CT scan based on the assumption that CT slice thickness is 5 mm or less. If CT scans have slice thickness greater than 5 mm, the minimum size for a measurable lesion should be twice the slice thickness. MRI is also acceptable in certain situations (e.g. for body scans).

Definitions

Evaluable for toxicity. All patients will be evaluable for toxicity from the time of their first treatment with *MK-3475 and afatinib*.

Evaluable for objective response. Only those patients who have measurable disease present at baseline, have received at least one cycle of therapy, and have had their disease re-evaluated will be considered evaluable for response. These patients will have their response classified according to the definitions stated below. (Note: Patients who exhibit objective disease progression prior to the end of cycle 1 will also be considered evaluable.)

Evaluable Non-Target Disease Response. Patients who have lesions present at baseline that are evaluable but do not meet the definitions of measurable disease, have received at least one cycle of therapy, and have had their disease re-evaluated will be considered evaluable for non-target disease. The response assessment is based on the presence, absence, or unequivocal progression of the lesions.

Disease Parameters

Measurable disease. Measurable lesions are defined as those that can be accurately measured in at least one dimension (longest diameter to be recorded) as ≥ 20 mm by chest x-ray or as ≥ 10 mm with CT scan, MRI, or calipers by clinical exam. All tumor measurements must be recorded in millimeters (or decimal fractions of centimeters).

Note: Tumor lesions that are situated in a previously irradiated area are measurable if there is evidence of growth post-radiation such as increase in size on CT or increase in FDG avidity on PET.

Malignant lymph nodes. To be considered pathologically enlarged and measurable, a lymph node must be ≥ 15 mm in short axis when assessed by CT scan (CT scan slice thickness recommended to be no greater than 5 mm). At baseline and in follow-up, only the short axis will be measured and followed.

Non-measurable disease. All other lesions (or sites of disease), including small lesions (longest diameter <10 mm or pathological lymph nodes with ≥ 10 to <15 mm short axis), are considered non-measurable disease. Bone lesions, leptomeningeal disease, ascites, pleural/pericardial effusions, lymphangitis cutis/pulmonitis, inflammatory breast disease, and abdominal masses (not followed by CT or MRI), are considered as non-measurable.

Note: Cystic lesions that meet the criteria for radiographically defined simple cysts should not be considered as malignant lesions (neither measurable nor non- measurable) since they are, by definition, simple cysts.

‘Cystic lesions’ thought to represent cystic metastases can be considered as measurable lesions, if they meet the definition of measurability described above. However, if non-cystic lesions are present in the same patient, these are preferred for selection as target lesions.

Target lesions. All measurable lesions up to a maximum of 2 lesions per organ and 5 lesions in total, representative of all involved organs, should be identified as **target lesions** and recorded and measured at baseline. Target lesions should be selected on the basis of their size (lesions with the longest diameter), be representative of all involved organs, but in addition should be those that lend themselves to reproducible repeated measurements. It may be the case that, on occasion, the largest lesion does not lend itself to reproducible measurement in which circumstance the next largest lesion that can be measured reproducibly should be selected. A sum of the diameters (longest for non-nodal lesions, short axis for nodal lesions) for all target lesions will be calculated and reported as the baseline sum diameters. If lymph nodes are to be included in the sum, then only the short axis is added into the sum. The baseline sum diameters will be used as reference to further characterize any objective tumor regression in the measurable dimension of the disease.

Non-target lesions. All other lesions (or sites of disease) including any measurable lesions over and above the 5 target lesions should be identified as **non-target lesions** and should also be recorded at baseline. Measurements of these lesions are not required, but the presence, absence, or in rare cases unequivocal progression of each should be noted throughout follow-up.

Response Criteria

Evaluation of Target Lesions

Complete Response (CR): Disappearance of all target lesions. Any pathological lymph nodes (whether target or non-target) must have reduction in short axis to <10 mm.

Partial Response (PR): At least a 30% decrease in the sum of the diameters of target lesions, taking as reference the baseline sum diameters.

Progressive Disease (PD): At least a 20% increase in the sum of the diameters of target lesions, taking as reference the smallest sum on study (this includes the baseline sum if that is the smallest on study). In addition to the relative increase of 20%, the sum must also demonstrate an absolute increase of at least 5 mm. (Note: the appearance of one or more new lesions is also considered progressions).

Stable Disease (SD): Neither sufficient shrinkage to qualify for PR nor sufficient increase to qualify for PD, taking as reference the smallest sum diameters while on study.

Evaluation of Non-Target Lesions

Complete Response (CR): Disappearance of all non-target lesions and normalization of tumor marker level. All lymph nodes must be non-pathological in size (<10 mm short axis).

Note: If tumor markers are initially above the upper normal limit, they must normalize for a patient to be considered in complete clinical response.

Non-CR/Non-PD: Persistence of one or more non-target lesion(s) and/or maintenance of tumor marker level above the normal limits.

Progressive Disease (PD): Appearance of one or more new lesions and/or *unequivocal progression* of existing non-target lesions. *Unequivocal progression* should not normally trump target lesion status. It must be representative of overall disease status change, not a single lesion increase.

Although a clear progression of “non-target” lesions only is exceptional, the opinion of the treating physician should prevail in such circumstances, and the progression status should be confirmed at a later time by the review panel (or Principal Investigator).

Evaluation of Best Overall Response

The best overall response is the best response recorded from the start of the treatment until disease progression/recurrence (taking as reference for progressive disease the smallest measurements recorded since the treatment started). The patient's best response assignment will depend on the achievement of both measurement and confirmation criteria.

For Patients with Measurable Disease (i.e., Target Disease)

Target Lesions	Non-Target Lesions	New Lesions	Overall Response	Best Overall Response when Confirmation is Required*
CR	CR	No	CR	≥4 wks. Confirmation**
CR	Non-CR/Non- PD	No	PR	≥4 wks. Confirmation**
CR	Not evaluated	No	PR	
PR	Non-CR/Non- PD/not evaluated	No	PR	
SD	Non-CR/Non-PD/not evaluated	No	SD	Documented at least once >4 wks. from baseline**
PD	Any	Yes or No	PD	No prior SD, PR or CR
Any	PD***	Yes or No	PD	
Any	Any	Yes	PD	

* See RECIST 1.1 manuscript for further details on what is evidence of a new lesion.
** Only for non-randomized trials with response as primary endpoint.
*** In exceptional circumstances, unequivocal progression in non-target lesions may be accepted as disease progression.
Note: Patients with a global deterioration of health status requiring discontinuation of treatment without objective evidence of disease progression at that time should be reported as "*symptomatic deterioration*." Every effort should be made to document the objective progression even after discontinuation of treatment.

For Patients with Non-Measurable Disease (i.e., Non-Target Disease)

Non-Target Lesions	New Lesions	Overall Response
CR	No	CR
Non-CR/non-PD	No	Non-CR/non-PD*
Not all evaluated	No	not evaluated
Unequivocal PD	Yes or No	PD
Any	Yes	PD

* 'Non-CR/non-PD' is preferred over 'stable disease' for non-target disease since SD is increasingly used as an endpoint for assessment of efficacy in some trials so to assign this category when no lesions can be measured is not advised

Duration of Response

Duration of overall response: The duration of overall response is measured from the time measurement criteria are met for CR or PR (whichever is first recorded) until the first date that recurrent or progressive disease is objectively documented (taking as reference for progressive disease the smallest measurements recorded since the treatment started).

The duration of overall CR is measured from the time measurement criteria are first met for CR until the first date that progressive disease is objectively documented.

Duration of stable disease: Stable disease is measured from the start of the treatment until the criteria for progression are met, taking as reference the smallest measurements recorded since the treatment started, including the baseline measurements.

Progression-Free Survival

PFS is defined as the duration of time from start of treatment to time of progression or death, whichever occurs first.

Response Review

Response review will be done by the investigator.

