Pneumonitis	2	Toxicity resolves to Grade 0-1	Toxicity does not resolve within 12 weeks of last dose or inability to reduce corticosteroid to 10 mg or less of prednisone or equivalent per day within 12 weeks
	3-4	Permanently discontinue	Permanently discontinue
Renal Failure or Nephritis	2	Toxicity resolves to Grade 0-1	Toxicity does not resolve within 12 weeks of last dose or inability to reduce corticosteroid to 10 mg or less of prednisone or equivalent per day within 12 weeks
	3-4	Permanently discontinue	Permanently discontinue
All Other Drug-Related Toxicity ^c	3 or Severe	Toxicity resolves to Grade 0-1	Toxicity does not resolve within 12 weeks of last dose or inability to reduce corticosteroid to 10 mg or less of prednisone or equivalent per day within 12 weeks
	4	Permanently discontinue	Permanently discontinue

Note: Permanently discontinue for any severe or Grade 3 drug-related AE that recurs or any life-threatening event.

^a For patients with liver metastasis who begin treatment with Grade 2 AST or ALT, if AST or ALT increases by greater than or equal to 50% relative to baseline and lasts for at least 1 week then patients should be discontinued.

^b If symptoms resolve within one hour of stopping drug infusion, the infusion may be restarted at 50% of the original infusion rate (e.g., from 100 mL/hr to 50 mL/hr). Otherwise dosing will be held until symptoms resolve and the subject should be premedicated for the next scheduled dose; Refer to Infusion Treatment Guidelines for further management details.

^c Patients with intolerable or persistent Grade 2 drug-related AE may hold study medication at physician discretion. Permanently discontinue study drug for persistent Grade 2 adverse reactions for which treatment with study drug has been held, that do not recover to Grade 0-1 within 12 weeks of the last dose.

Dosing interruptions are permitted in the case of medical / surgical events or logistical reasons not related to study therapy (e.g., elective surgery, unrelated medical events, patient vacation, and/or holidays). Subjects should be placed back on study therapy within 3 weeks of the scheduled interruption, unless otherwise discussed with the Sponsor. The reason for interruption should be documented in the patient's study record.

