5.4 Attribution of Adverse Events

Investigators are required to assess whether there is a reasonable possibility that afatinib and/or MK-3475 caused or contributed to the adverse event. The following general guidance may be used.

- Definite – The AE is *clearly related* to the study treatment.
- Probable – The AE is *likely related* to the study treatment.
- Possible – The AE *may be related* to the study treatment.
- Unlikely – The AE is *doubtfully related* to the study treatment.
- Unrelated – The AE is *clearly NOT related* to the study treatment.

If an adverse event is attributable (either definite, probable or possible) to MK-3475 and/or afatinib that requires the drug be held the other drug may be continued if it the adverse event is not attributable to that drug (either unlikely or unrelated) with approval of the treating physician and primary investigator. Exceptions include pneumonitis and grade 2 and above enterocolitis (as defined in this protocol) where both MK-3475 and afatinib must be held.

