2. In general, the window for each visit is \pm 3 days unless otherwise specified.
3. For women of reproductive potential, a urine or serum pregnancy test will be performed within 72 hours prior to first dose of trial treatment. If urine pregnancy results cannot be confirmed as negative, a serum pregnancy test, performed by the local study site laboratory, will be required. Pregnancy tests (serum and/or urine tests) should be repeated if required by local guidelines.
4. Coagulation factors (PT/INR and aPTT) should be monitored closely throughout the trial for any subject receiving anticoagulant therapy.
5. Laboratory tests for screening are to be performed within 10 days prior to the first dose of trial treatment.
6. After Cycle 1, lab samples can be collected up to 72 hours prior to the scheduled time point. Laboratory results must be known and acceptable prior to dosing.
7. The initial tumor imaging will be performed within 30 days prior to the first dose of trial treatment. Scans performed as part of routine clinical management are acceptable for use as the screening scan if they are of diagnostic quality and performed within 30 days prior to the first dose of trial treatment. On-study imaging will be performed every 6 weeks (42 -7 days) after the first dose of trial treatment or more frequently if clinically indicated. The timing for imaging studies should follow calendar days and should not be adjusted for delays in cycle starts or extension of MK-3475/afatinib cycle frequencies. The same imaging technique should be used in a subject throughout the trial. CT including the chest, abdomen and pelvis or PET-CT is required for the baseline assessment.
8. Provide documentation of the subject's tumor EGFR mutation from a CLIA certified laboratory.
9. MK-3475 can be administered for up to 2 years. For the dose de-escalation and Cohort (Arm) A (concurrent afatinib and MK-3475) both drugs will be administered as outlined in this protocol starting with cycle #1. For cohort B. MK-3475 will be initiated with cycle #1 and afatinib will commence in combination with MK-3475 starting with cycle #3.
10. Tumor biopsy for immune and EGFR biomarker analysis will be performed prior to Cycle 1 of treatment either on archival tissue or fresh biopsy (within 60 days). Repeat biopsy will be performed prior to initiation of cycle 3 (42 days (-7 days))

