8.0 STATISTICAL ANALYSIS PLAN

8.1 Statistical Analysis Plan Summary

This is a phase I/Ib study. A minimum of 9 patients, if trial is terminated early due to unacceptable toxicity and a maximum of 38 patients (18 patients in the dose de-escalation cohort plus 10 in each of the two expansion cohorts) are anticipated for this trial. Analysis of safety and biomarkers will be limited to patients who receive active treatment.

The dose de-escalation phase will establish a MTD recommended dose of MK-3475 in combination with lead in MK-3475 followed by the combination or concurrent afatinib/MK-3475.

We plan to enter 3 patients at Dose Level 0. If 0/3 or 1/3 patients experience a DLT on level 0, an additional 3 patients will be accrued to Level 0, where 2 or more DLTs will terminate that study arm and we will proceed to dose level -1.

If 2 or more patients have DLTs at level 0, patients will be accrued at level -1. If 1/3 patients experience a DLT on level -1, an additional 3 patients will be accrued to Level -1, where 2 or more DLTs will require termination of that study arm while 1 DLT out of 6 will result in proceeding with dose level -1 as the MTD for the dose expansion cohorts.

If 2 or more patients have DLTs at level -1, patients will be accrued at level -2. If 1/3 patients experience a DLT on level -2, an additional 3 patients will be accrued to Level -2, where 2 or more DLTs will require termination of the study while 1 DLT out of 6 will result in proceeding with dose level -2 as the MTD for the dose expansion cohorts.

The phase I de-dose escalation portion of the trial will be closed when the maximum tolerated dose level (MTD) or dose level 0 is reached and six patients have been treated at that dose level.

Please see section 5.1.4.2 for further details.

All patients at a given dose level who have not experienced DLT, must be observed for a minimum of 21 days or until completion of their first cycle of therapy before the dose level can be escalated. Treatment will continue in an individual patient at the same dose level if no DLT is observed and if benefit is observed. There will be no dose escalation allowed for an individual patient.

The recommended phase II dose (RP2D) will be determined by the overall assessment of the MTD and toxicities observed in the de-dose escalation and dose expansion portion of this study.

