The baseline assumption is that single agent afatinib yields a response rate of 10% in this setting, and a response rate of 10% or less would not warrant further study. A response rate of 40% or greater would justify further study with a larger sample size. With 10 patients enrolled in cohort A expansion arm, we will declare this combination lacking promise if fewer than 3 patients respond, and potentially worthy of further study if 3 or more patients respond. If the true response rate is 10%, the chance of having 3 or more patients respond is 7%. If the true response rate is 40%, the

chance of having 3 or more patients respond is 83%.

If 3 or more patients respond, the response rate, toxicity, and progression-free survival will be evaluated to decide if larger randomized studies are warranted in this disease. Descriptive summaries will be provided for each of these summary measures (numbers and proportion responding, number and proportion with specific type and grade of toxicities, Kaplan-Meier plot and life-table summary of progression-free survival.) As stated earlier, a “pick the winner” approach between cohort A and cohort B based on toxicity: RR, PFS and changes in PDL1 expression will decide which dosing scheme to take further. It is assumed that a true RR >40% would be sufficient to recommend such development, provided safety and tolerability are also acceptable.

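### The A-versus-B response comparison has no stated denominator, and the evaluable-only rule in 7.1.2.6 drops treated patients who stop early and are never rescanned

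*Combined protocol and SAP*

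**What the plan says.** Section 7.1.2.6 sets one response rule for both cohorts. Patients with measurable disease who "have received at least one cycle of therapy, and have had their disease re-evaluated will be considered evaluable for response". A note adds that objective progression before the end of Cycle 1 also makes a patient evaluable. The same section defines toxicity evaluability: "All patients will be evaluable for toxicity from the time of their first treatment with *MK-3475 and afatinib".

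Section 8.1 is worded differently. On safety it says "Analysis of safety and biomarkers will be limited to patients who receive active treatment". Its response rule begins "With 10 patients enrolled in cohort A expansion arm" and asks for 3 or more responders. It then says that a "approach between cohort A and cohort B based on toxicity: RR, PFS and changes in PDL1 expression will decide which dosing scheme" to take further. No denominator is given for the response rate in that comparison.

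The cohorts differ in the first six weeks. Cohort A takes both drugs from Cycle 1. Cohort B takes MK-3475 alone for two cycles, and "afatinib will commence in combination with MK-3475 starting with cycle #3" (Section 6.1, note 9). Table 5 in 5.1.5.3 lists several toxicities that end MK-3475 for good, with the note "Permanently discontinue for any severe or Grade 3 drug-related AE that recurs or any life-threatening event". Section 5.4 says that when an event "requires the drug be held the other drug may be continued if it the adverse event is not attributable to that drug", subject to approvals.

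**The concern.** Requiring a re-evaluation removes patients for a reason tied to outcome and tolerability. Someone who stops for toxicity in the first weeks, moves to another therapy and misses the 6-week scan is a treatment failure for the schedule, yet would not appear in its response rate.

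This matters more in a comparison, because the route out of the denominator is not the same in both cohorts. A Cohort A patient who loses MK-3475 to an event not attributed to afatinib may stay on afatinib and be scanned on study. A Cohort B patient in the lead-in has no second drug to continue. Disease-status follow-up ends when new anticancer therapy starts (7.4.3.2), and 5.5.2 prohibits no therapy after study treatment. An evaluable-only rate can then favour Cohort B through who is counted and not through what the schedule does. At stake is one of the four criteria that 8.1 uses to choose a schedule.

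The toxicity definition has a related fault. Taken literally, it does not make a patient evaluable until both drugs have been given, so a Cohort B patient who stops in the lead-in is never evaluable for toxicity.

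**Working it through.** **1. The plan's own figures.** Inputs from 8.1: n = 10, threshold 3 responders, true rates 10% and 40%. The formula is P(X ≥ 3) for X ~ Binomial(10, p).
- p = 0.10 gives 0.0702; the plan states 7%.
- p = 0.40 gives 0.8327; the plan states 83%.

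Both reproduce. The rule is a count of responders among 10 enrolled, so removing an unscanned non-responder does not change that count. The exposure is in the A-versus-B rate.

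**2. Who leaves the response denominator.** From 7.1.2.6, by type of early stopper:
- Progressed before the end of Cycle 1: evaluable.
- Completed one cycle and was rescanned: evaluable, in either cohort. MK-3475 alone is the assigned therapy in Cohort B's first two cycles, so it is reasonably read as a cycle of therapy.
- Treated but never re-evaluated: not evaluable. This is the only group at issue.

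**3. Effect on one cohort's rate.** With r responders among 10 treated and m patients never re-evaluated, the all-treated rate is r/10 and the evaluable-only rate is r/(10 − m). The ratio is 10/(10 − m). For r = 4:
- m = 0: 4/10 = 40% on either basis.
- m = 1: 40% against 4/9 = 44.4%.
- m = 2: 40% against 4/8 = 50%.

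The documents give no value for m; 1 and 2 are assumptions.

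**4. Effect on the comparison.** Assume one permanent MK-3475 stop in each cohort. Let response be 40% on the combination, 10% for the Cohort A patient left on afatinib (the single-agent rate assumed in 8.1) and 0% for the Cohort B patient stopped in the lead-in. Expected rates:
- Cohort A: (9 × 0.40 + 0.10)/10 = 37%.
- Cohort B, stopper counted: (9 × 0.40)/10 = 36%, a difference of −1 point.
- Cohort B, stopper excluded: (9 × 0.40)/9 = 40%, a difference of +3 points.

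The sign can change, but the excluded case requires that the Cohort B stopper misses the scan and the Cohort A stopper does not. If both are excluded, the expected rates are 40% and 40%.

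**5. Toxicity.** On the literal wording of 7.1.2.6, one stopping event in a Cohort B lead-in becomes 0/9 instead of 1/10. Section 8.1 (patients receiving active treatment) and Section 7.5 (all adverse events reported from treatment allocation) point to 1/10, which is the likelier reading.

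**The case against.** The strongest reply is that 7.1.2.6 already supplies a rule for both cohorts and that few patients can fall outside it. Much of this stands.
- Under 5.8, patients who stop for reasons other than progression remain in disease follow-up. Section 6.1, note 7, ties imaging to calendar days with a window opening at day 35 (42 − 7) and allows earlier scans if clinically indicated.
- Under 7.1.1.5.3, new therapy within 30 days of the last dose must wait for the safety visit.
- Several Table 5 stops need 12 weeks without resolution, so they cannot occur within a 6-week lead-in.
- The asymmetry is not general. Section 5.4 holds both drugs for pneumonitis and for grade 2 or higher enterocolitis, Table 6 stops afatinib for confirmed ILD, and Table 7 ends trial treatment after a grade 3-4 infusion reaction. Early afatinib toxicity could also remove Cohort A patients, which would push the other way.

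A reader might infer that the missing rule materially biases the choice of schedule. The documents do not support that. On the assumptions of step 4, the exact chance that Cohort B shows the higher response rate (ties split) is 48.2% with its stopper counted and 57.6% with it excluded. That is an extreme case. Excluding the stopper in both cohorts gives 50.0%. If the Cohort B stopper has a 25% chance of missing the scan and the Cohort A stopper is always scanned, it is 0.75 × 48.2% + 0.25 × 57.6% = 50.5%.

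A reader might also infer a design fault in the silence on starting afatinib after a lead-in MK-3475 stop. Cohort B is defined only as lead-in followed by the combination, which suggests that afatinib would not start. Stating this is an optional clarification. Nor should Table 7 be narrowed to MK-3475 as a tidy-up: that would lift an existing bar on afatinib after a severe infusion reaction.

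What the reply leaves standing is that a treated, unscanned patient is dropped under 7.1.2.6, and that 8.1 does not say whether its comparison uses that set.

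**Conclusion.** The point holds as a minor one. The response definition excludes treated patients who are never re-evaluated, 8.1 names no denominator for the A-versus-B response rate, and the structure of the lead-in allows such losses to differ between cohorts in a way that can favour Cohort B. The size is unknown and probably small: it depends on how many patients stop within six weeks and miss the scan, and the documents give neither figure.

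No stated error rate or threshold is affected. The comparison is non-randomized, sequential, limited to 10 patients per cohort and based on toxicity, response, PFS and PD-L1 change together, so response is one input among several. The toxicity wording in 7.1.2.6 does not fit the Cohort B lead-in, although 8.1 already points to the sensible reading. PFS runs from the start of treatment and is not limited to evaluable patients; naming its analysis set simply keeps the criteria aligned.

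**What to change.** 1. Add to 8.1: for the choice between Cohorts A and B, every expansion patient who received any study drug counts in response rate, toxicity and PFS; a patient with no re-evaluation counts as a non-responder; the evaluable set of 7.1.2.6 is reported as supportive only.
2. In 7.1.2.6, make toxicity evaluable from the first dose of MK-3475 or afatinib, whichever comes first, so that it agrees with 8.1.
3. Optional: state whether a Cohort B patient who permanently stops MK-3475 in the lead-in may start afatinib on study. Either answer is workable.

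The cost is a few lines of text, with no added patients, visits or forms. Reported response rates may be slightly lower than on the evaluable set. The text should be settled before Cohort B data are seen.
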